3.2 DETERMINATION OF SAMPLE SIZE

The study is planned to enroll approximately 50 subjects. The sample size will enable a statistical power of 80%, at 1-sided significance level of 0.025, to test against the null hypothesis of endoscopic improvement rate of 12%, assuming the endoscopic improvement rate for PRA023 is 27%.

The null hypothesis of an endoscopic improvement (decrease in SES-CD $\geq 50\%$) rate of 12% is based on a meta-analysis estimate of the upper limit of 95% CI of the observed placebo rate (95% CI) of 9.5% (7.1, 11.9) from multiple modern-era CD clinical trials with centrally read endoscopy and similar eligibility criteria. [1]

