3.3 RANDOMIZATION

3.3.1 RANDOMIZATION NUMBERS

This is an open-label study where all subjects will receive PRA023. Eligible subjects will be assigned a subject number by the IRT system at Week 0/Day 1 upon confirmation of study eligibility as a means to track the number of eligible subjects enrolled in the study. Subjects who are randomized in OLE will retain their original subject numbers.

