6.3.2 CONTINUOUS ENDPOINTS

The mean change from baseline in SES-CD score at Week 12 for PP analysis set will be estimated using ANCOVA with baseline SES-CD score as covariates. The 95% confidence interval for the LS mean for the change from baseline at Week 12 will be calculated. The median for the change from baseline in SES-CD score at Week 12 for PP analysis set will also be estimated and p-value for testing against no change will be reported using Wilcoxon rank test.

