6.4.2 CONTINUOUS EFFICACY ENDPOINTS

The definition of the continue efficacy endpoints (Mean Change from Baseline) by visit are listed in Table 5 below.

Table 5 Definition of Exploratory Continuous Endpoints

Measure	Definition	Analysis Timepoint
SES-CD segment score	Mean change from baseline	Week 12
PD markers (TL1A concentrations, fecal calprotectin, and hsCRP)	Mean fold change from baseline	Over time
RHI	Mean change in Roberts Histopathology Index (RHI) from baseline	Week 12
GHAS	Mean change in global histological activity score (GHAS) from baseline	Week 12
PDAI	Mean change in Perianal Disease Activity Index(PDAI) subscore from baseline	Week 12
CDAI	Mean change in CDAI and components from Baseline over time	Over time
PRO-2	Mean change in PRO-2 over time	Over time
IBDQ	Mean change from baseline in IBDQ score over time	Over time

Abbreviations: CDAI, Crohn's disease activity index; hsCRP, High sensitivity C-reactive protein; PRO-2, Two component patient-reported outcome; RHI, Roberts Histopathology Index; GHAS, Global histological activity score; SES-CD, Simple endoscopy score for Crohn's disease; PDAI, Perianal Disease Activity Index; IBDQ, Inflammatory Bowel Disease Questionnaire.

In general, continuous endpoints will be summarized using descriptive statistics of the values at each visit and the change from baseline to each post-baseline visit. Missing data will not be imputed for descriptive statistics.

The mean change in CDAI over time through Week 12, mean change in PRO-2 over time through Week 12 and mean change in IBDQ score over time through Week 12 will be estimated according to a MMRM model with baseline CDAI, visit as fixed effect and subject as random effect. The 95% confidence intervals at each time point will be calculated according to the MMRM model. This analysis will be conducted by maximum likelihood methods using the SAS PROC MIXED procedure.

Additional descriptive summary over time will be reported for patients who entered OLE based on available data as of cutoff date of the DBL for Induction period.

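### The MMRMs for change in PRO-2 and IBDQ adjust for baseline CDAI, not each outcome's own baseline; the cost is a small missing-data bias and slightly short intervals, not lost precision

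*SAP*

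**What the plan says.** SAP section 6.4.2 covers three outcomes with one model sentence: change in CDAI, "mean change in PRO-2 over time through Week 12" and "mean change in IBDQ score over time through Week 12". The specification is an "MMRM model with baseline CDAI, visit as fixed effect and subject as random effect", and "This analysis will be conducted by maximum likelihood methods using the SAS PROC MIXED procedure". Baseline CDAI is the only baseline covariate named. No other part of the SAP or protocol substitutes baseline PRO-2 or baseline IBDQ. SAP section 10 says only that MMRM will be used.

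SAP section 6.3.2 takes the other approach for the endoscopic score: change in SES-CD "will be estimated using ANCOVA with baseline SES-CD score as covariates".

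The own baselines are available. IBDQ is scheduled at Weeks 0, 6 and 12 (SAP section 8.1). PRO-2 is built from two CDAI diary items (section 6.1.2.1). The FAS requires a baseline CDAI (section 4.2.3), which counts as missing if any component is missing (section 6.1.2), so FAS subjects should have the items for a baseline PRO-2.

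**The concern.** Baseline CDAI is an indirect stand-in for the starting level of the other two outcomes. It is closer for PRO-2, which shares two of its items, than for IBDQ, which also covers emotional and social function. Entry limits CDAI to 220 to 450, which narrows the covariate further.

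For these endpoints the likelihood model is also the missing-data method, since the descriptive summaries are not imputed. If subjects drop out according to their own starting PRO-2 or IBDQ, a model that conditions on baseline CDAI only partly accounts for it, and the visit means can shift. IBDQ has only two post-baseline visits from which to recover the missing information.

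A second matter is what the 95% interval describes. With any baseline entered as a covariate, the model standard error treats the observed baselines as fixed, so the interval is too short for the population mean change.

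**Working it through.** **What the plan supplies.** About 50 subjects (SAP section 3.2), one arm in induction (section 3.3.1), IBDQ at Weeks 0, 6 and 12, and PRO-2 at baseline and five later visits (Weeks 1, 2, 6, 10, 12). It gives no SD, correlation, precision target or missing rate for these models, so there is no planned figure to reproduce.

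**Assumptions.** ρ is the correlation of the outcome's own baseline with its later values. c is the absolute correlation of baseline CDAI with that own baseline. The SD is equal at baseline and follow-up, and baseline CDAI predicts change only through the own baseline. Simulations: ρ = 0.3 or 0.5; c = 0.5 for IBDQ and 0.7 for PRO-2; correlation 0.7 among post-baseline visits; either complete data or 25% missing at Week 12.

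**Step 1: true error with complete data.** A least-squares (LS) mean taken at the average covariate equals the raw mean change, whichever covariate is used. In SD units its standard error is √[2(1−ρ)/n]. With n = 50 this is √(1.4/50) = 0.167 for ρ = 0.3 and √(1.0/50) = 0.141 for ρ = 0.5. The covariate does not enter.

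**Step 2: the printed error.** The own baseline explains (1−ρ)/2 of the variance of change, and baseline CDAI explains c²(1−ρ)/2. The interval-width ratio, CDAI model to own-baseline covariate, is √{[1 − c²(1−ρ)/2] / [1 − (1−ρ)/2]}. For ρ = 0.5 and c = 0.6 this is √(0.91/0.75) = 1.10. Over ρ = 0.3 to 0.7 and c = 0.4 to 0.8 it runs from 1.03 to 1.21. Only the printed interval changes, not the error in step 1.

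**Step 3: simulation, complete data** (random intercept, maximum likelihood, n = 50, 1,500 runs per scenario, SD units).

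| Scenario | True SE, either covariate | Printed SE: CDAI / own | Coverage: CDAI / own |
|---|---|---|---|
| IBDQ, ρ 0.3 | 0.166 | 0.156 / 0.132 | 93.3% / 87.8% |
| IBDQ, ρ 0.5 | 0.143 | 0.133 / 0.119 | 92.5% / 88.9% |
| PRO-2, ρ 0.5 | 0.145 | 0.130 / 0.120 | 92.1% / 89.6% |

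Both printed errors fall short of the true one, and the own-baseline covariate falls further short. The own-baseline PRO-2 row has the same form as the planned CDAI model (five visits, own baseline as covariate), so CDAI carries the same under-coverage under these assumptions.

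**Step 4: 25% missing at Week 12, completely at random.** True SEs are 0.151 (CDAI) and 0.150 (own) for IBDQ at ρ 0.5, and 0.148 for both in PRO-2.

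**Step 5: 25% missing at Week 12, dependent on own baseline** (bias in SD units).

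| Scenario | CDAI, LS mean at FAS baseline mean | Own, at FAS baseline mean | CDAI, at mean over analysed records | Own, at mean over analysed records |
|---|---|---|---|---|
| IBDQ, ρ 0.3 | 0.026 | −0.004 | 0.045 | 0.068 |
| IBDQ, ρ 0.5 | 0.024 | −0.005 | 0.038 | 0.047 |
| PRO-2, ρ 0.5 | 0.014 | 0.002 | 0.040 | 0.054 |

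At the FAS mean, the bias under the planned model is 0.026/0.177 = 0.15, 0.024/0.154 = 0.16 and 0.014/0.149 = 0.09 of a standard error.

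**Step 6: own baseline as the first repeated measure** (IBDQ layout, unstructured covariance, maximum likelihood, ρ 0.3 to 0.5, 6,000 runs). With about 26% missing driven by own baseline, bias was at most 0.002 SD and coverage 94 to 95%. With complete data, coverage was also 94 to 95%. This route has no covariate mean to choose. The six-occasion PRO-2 layout was not part of this run.

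**The case against.** The strongest objection is to the inference a reader might draw first, that adjusting for the wrong baseline loses precision. If own baseline correlates 0.4 to 0.6 with change and baseline CDAI 0.2, then √[(1−r²)/(1−0.2²)] gives 0.94 to 0.82, a model standard error 6 to 18% smaller. That argument belongs to a between-arm contrast. Here "This is an open-label study where all subjects will receive PRA023" and one mean change is estimated, so the percentage describes only the conditional standard error. Taking the smaller value as a gain would mean an interval that covers less often (88 to 90% against 92 to 93%). This objection stands in full.

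Second, simply swapping the covariate need not remove the bias. With LS means at the mean over analysed records, own baseline does worse than CDAI (0.047 to 0.068 SD against 0.038 to 0.045 SD). This stands, and it determines the form of the fix.

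Third, the effect is small. Other visits of the same outcome already carry part of the information, the endpoints lie outside the tested hierarchy (SAP section 6.10), section 6.4.2 names no test for these models, and covariate-free summaries of change are reported at each visit. All of this is correct and limits the weight of the point.

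Fourth, the sentence may be loose drafting for the respective baseline, and for CDAI it already names the right one. That is possible, but nothing in the documents says so, and a programmer following the text would fit baseline CDAI to IBDQ.

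**Conclusion.** The point holds as a minor improvement to exploratory analyses. Read literally, the SAP models PRO-2 and IBDQ change without the outcome's own baseline, unlike its SES-CD analysis. No real precision is lost. What remains is a bias of about 0.01 to 0.03 SD, at most about a sixth of a standard error, and intervals that leave out baseline sampling variation. The bias figure assumes 25% missing at Week 12 dependent on own baseline, LS means at the FAS baseline mean, and the correlations listed above. The documents give none of these, and with missingness completely at random neither model is materially biased.

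A reader might also infer that the exploratory results are unreliable or that the trial's conclusion is at risk. The documents do not support that: the primary endpoint and the one tested secondary endpoint are binary and do not use this model.

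**What to change.** Replace the model sentence in SAP section 6.4.2. For each of CDAI, PRO-2 and IBDQ, fit the outcome itself with baseline as the first repeated measure, visit as a fixed effect and unstructured covariance across visits, and report visit-minus-baseline contrasts with 95% confidence intervals. CDAI is included because its planned interval is also conditional on baseline.

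If a covariate is kept, name the respective outcome's own baseline, evaluate LS means at the FAS baseline mean, and state that the interval is conditional on the observed baselines and covers less often.

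The cost is one SAP sentence and no new data. Unstructured covariance needs 3 × 4/2 = 6 parameters for IBDQ and 6 × 7/2 = 21 for PRO-2 and CDAI, against 2 for a random intercept, so a fallback structure should be named in case of non-convergence. The printed PRO-2 and IBDQ intervals widen slightly. With complete data the ratio is 1/√[1 − c²(1−ρ)/2]: 1.05 (ρ 0.3, c 0.5), 1.03 (ρ 0.5, c 0.5) and 1.07 (ρ 0.5, c 0.7). SAP section 1 already provides for documenting later changes, with rationale, in the clinical study report.

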4 GENERAL CONSIDERATIONS FOR DATA ANALYSES

4.1 REPORTING CONVENTIONS

The following reporting conventions apply generally to tables, listings, and graphs:

- Unless otherwise specified, the baseline value is defined as the last non-missing assessment before the first does of study treatment.
- If the date of interest occurs on or after the first dose date, the study day will be calculated as (date of interest – date of first dose) + 1.
- If the date of interest occurred prior to the first dose date, then study day will be calculated as (date of interest – date of first dose).
- Categorical data will be summarized by treatment group in terms of frequency counts and percentages.
- Continuous variables will be summarized by treatment group using descriptive statistics (the number of subjects (n), mean, median, standard deviation (SD), minimum (Min), and maximum (Max)) of the values at each visit and the change from baseline to each visit, unless specified otherwise.
- Confidence Intervals (CIs) will be presented as 2-sided 95% CIs.
- All mean, median and CI values will be formatted to one more decimal place than the measured values. SD values will be formatted to two more decimal places than the measured value. Min and Max will be formatted to the same number of decimal places as the measured value. The maximum number of decimal places reported shall be four for any summary statistic.
- All percentages will be rounded to one decimal place, unless specified otherwise. The number and percentage of responses will be presented in the form xx (xx.x), where the percentage is in the parentheses.
- Change from baseline is calculated as a post-baseline value minus the baseline value.
- All laboratory data will be reported using standard international units.
- All analysis and summary tables will include the analysis population sample size (ie, number of subjects) in the column headings.

- By-subject listings will be presented for all subjects in the relevant analysis sets, and sorted by treatment allocation, study site (if applicable), Subject ID, date, and visit. Numeric data will be listed to the same number of decimal places as recorded on the eCRF or other data source. Data collected on log forms, such as AEs, will be presented in chronological order within the subject, and age, and sex will be included in the listing, as space permits.

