6.10 MULTIPLICITY

A closed hierarchical procedure will be used to control for multiple comparisons for the primary endpoint and the first secondary endpoint. The order of testing will be primary endpoint, followed by the secondary endpoint of clinical remission at Week 12. If the null hypothesis for the primary endpoint is not rejected, the testing procedure will be terminated. The subsequent analysis of clinical remission would be considered exploratory.

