8 OTHER ANALYSES

8.1 QUALITY OF LIFE(QOL)

The Inflammatory Bowel Disease Questionnaire (IBDQ) is a self-administered, disease-specific Health-Related Quality of Life (HRQOL) instrument for patients with IBD. [11] The IBDQ covers 4 dimensions: bowel symptoms (10 items, questions 1, 5, 9, 13, 17, 20, 22, 24, 26, and 29), systemic symptoms (5 items, questions 2, 6, 10, 14 and 18), emotional function (12 items, questions 3, 7, 11,15, 19, 21, 23, 27, 30, 31 and 32), and social function (5 items, questions 4, 8, 12, 16, and 28). Items are scored on a 7-point Likert scale, for a total global score in the range 32 to 224 (with higher scores indicating better HRQOL).

IBDQ scores will be collected at Week 0 Visit, Week 6 Visit, and Week 12 Visit. Summary statistics of the absolute and change from baseline scores for IBDQ total score and each subscale score will be displayed by treatment group and visit.

IBDQ Scores will be calculated as follows:

- The question on the same day of measurement will be used for calculation of each subscore and total score.
- For each subscore, sum of the questions will be round off to the first decimal place.
- IBDQ total score: sum of all questions and round off to the first decimal places.
- The value of each question after imputing missing data will be used for the calculation of each subscore.

The instructions on how the IBDQ score is calculated in the presence of missing or incomplete information is provided below with detailed scenarios given in Table 9. Rules for handling missing data:

1. If no response is given for a particular question and only one response per dimensional score is missing, impute the missing value to be equal to the mean score for that other item of the subscore
2. If two or more questions are unanswered for a particular domain, then the subscore will be set to missing.

If after steps 1 and 2, more than 4 questions are missing for the full IBQD, then the total IBDQ will be set to missing.

Table 9 IBDQ Missing Data Instructions

	Number of Missing Values				Comments/Actions
	Subscore 1	Subscore 2	Subscore 3	Subscore 4	
Scenario A	0	0	0	0	We can compute 4 subscores and the full IBDQ
Scenario B	1	0	0	0	We can compute both the full IBDQ and the 4 subscores, by replacing the missing value with the average mean (computed on the data available for its own subscore)

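### The MMRM in SAP 6.4.2 names a random subject effect but no within-subject covariance; coded as written, it gives every visit the same variance, so by-visit 95% intervals are miscalibrated if the spread of change differs by visit

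*SAP*

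**What the plan says.** SAP 6.4.2 plans, for mean change in CDAI, PRO-2 and IBDQ through Week 12, an "MMRM model with baseline CDAI, visit as fixed effect and subject as random effect". On estimation it says: "This analysis will be conducted by maximum likelihood methods using the SAS PROC MIXED procedure". On precision it says: "The 95% confidence intervals at each time point will be calculated according to the MMRM model". SAP 4.1 sets the convention: "Confidence Intervals (CIs) will be presented as 2-sided 95% CIs".

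The random subject effect is the only within-subject element written down. Section 6.4.2 gives no repeated-factor specification, covariance type, degrees-of-freedom method or fallback for non-convergence. The entries on this model in SAP 10 (Changes from Protocol) add none; one of them mentions a 95% interval for the least-squares mean change at Week 12.

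Two other provisions bear on how much this matters. The testing hierarchy in SAP 6.10 is limited: "A closed hierarchical procedure will be used to control for multiple comparisons for the primary endpoint and the first secondary endpoint". And SAP 6.4.2 also plans a model-free summary: "In general, continuous endpoints will be summarized using descriptive statistics of the values at each visit and the change from baseline to each post-baseline visit".

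**The concern.** A random subject intercept with a homogeneous residual is compound symmetry. The total variance at each visit is the between-subject variance plus the residual variance, and that sum is the same at Week 1 as at Week 12. The standard error of the mean at any visit is then built from a variance averaged over all visits.

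That is harmless if the spread of change is the same at each visit. If it is not, the interval is too narrow where the spread is above average and too wide where it is below. A rising spread is plausible here, though the documents do not show it. Week 1 falls on Day 8 and is scored from the preceding seven diary days. Under SAP 6.1.2 the look-back can extend to ten days, which at Day 8 reaches before the first dose. By Week 12, subjects will have separated into responders and non-responders. In that case the Week 12 interval would be the one that looks more precise than it is.

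**Working it through.** **Inputs from the documents.** About 50 subjects in a single arm (SAP 3.2). Post-baseline CDAI visits at Weeks 1, 2, 6, 10 and 12, so five (SAP Appendix G). For IBDQ, SAP 8.1 says "IBDQ scores will be collected at Week 0 Visit, Week 6 Visit, and Week 12 Visit", so two post-baseline visits. SAP 6.4.2 states no numerical figure for this model, so there is none to reproduce.

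**Inputs that are assumptions.** The documents give no SD and no between-visit correlation for change in any of the three scores. All SDs below are assumed. The correlation in the tables is 0.4; results at 0.6 were nearly the same. Data are complete; dropout was not examined.

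**Formula.** With complete data and J visits, the random-intercept model estimates one total variance, which is close to the mean of the visit variances:

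pooled SD = sqrt[(SD₁² + … + SD_J²) / J]

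The nominal 95% interval at visit j uses pooled SD/√n, while the true standard error is SD_j/√n. Ignoring estimation error,

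coverage at visit j ≈ 2Φ(1.96 × pooled SD / SD_j) − 1.

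**Numbers put in.** For SDs of 50, 60, 80, 90 and 95: the squares sum to 2500 + 3600 + 6400 + 8100 + 9025 = 29,625; divided by 5, 5925; square root 76.97. The ratio at Week 12 is 76.97/95 = 0.810, so coverage ≈ 2Φ(1.588) − 1 = 88.8%. At Week 1 the ratio is 76.97/50 = 1.539 and coverage is about 99.7%.

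**Simulation.** 4000 trials per case, n = 50. Width is the mean width of the Week 12 interval. The by-visit column is what an unstructured covariance gives with complete data.

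| SDs, Weeks 1, 2, 6, 10, 12 | Pooled SD / Week 12 SD | ML width (coverage) | REML width (coverage) | By-visit width (coverage) | Week 1 coverage, ML |
|---|---|---|---|---|---|
| 85 throughout | 1.000 | 46.6 (94.4%) | 47.3 (94.8%) | 48.3 (94.9%) | 94.6% |
| 70, 75, 85, 88, 90 | 0.911 | 44.9 (91.4%) | 45.6 (92.0%) | 51.2 (94.9%) | 97.6% |
| 50, 60, 80, 90, 95 | 0.810 | 42.2 (87.6%) | 42.8 (88.0%) | 54.0 (94.9%) | 99.7% |
| 40, 55, 80, 95, 100 | 0.775 | 42.5 (85.8%) | 43.1 (86.5%) | 56.8 (94.9%) | above 99.9% |
| 95, 90, 80, 75, 70 | 1.179 | 45.2 (97.4%) | 45.9 (97.7%) | 39.8 (94.9%) | 90.4% |

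In the three rising cases the Week 12 interval is 12% (44.9/51.2), 22% (42.2/54.0) and 25% (42.5/56.8) narrower than the by-visit interval. In the falling case it is 14% wider (45.2/39.8).

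A separate simulation with a baseline covariate and other rising paths gave Week 12 coverage of 91%, 89% and 87% for SDs going from 70 to 92, 55 to 95 and 45 to 100. Week 1 coverage was 97% to 99.9%. SDs falling from 95 to 70 gave 97.6% at Week 12 and 91% at Week 1.

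**Which element is responsible.** Replacing ML by REML widens the interval by about 1.5% (42.8/42.2, for example) and moves Week 12 coverage by 0.3 to 0.7 points. The rest comes from the common variance. A direct mixed-model fit (SD 50 to 95, correlation 0.5) shows this: the ML standard error was 10.5 at both Week 1 and Week 12, while the by-visit standard errors were 6.9 and 13.3.

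**IBDQ.** With two visits, SDs of 28 and 35 and correlation 0.6, Week 12 coverage was 91.4% (width 17.6) under the random intercept with ML, against 94.6% (19.8) by visit.

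**The case against.** The strongest reply is that the text is incomplete rather than wrong. It calls the model an MMRM, and many analysts would read that as a repeated factor with visit-specific variances. Nothing in SAP 6.4.2 excludes that structure, and the generic reference to likelihood methods may include REML. This stands as far as it goes. A reader might infer that the SAP forces one variance on all visits, but the documents do not say so. Compound symmetry is what results from coding the one element that is written. Equally, nothing in the text leads the programmer to any other structure.

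A reader might also infer that the maximum likelihood sentence is the cause. It is not: likelihood estimation imposes no common variance, and its own effect in 50 subjects is about half a point of coverage.

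A third tempting inference is that the Week 12 interval is simply too narrow. That holds only if the SD of change rises over the visits, which the documents neither state nor allow one to check. If the SD falls, the error reverses.

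Finally, little depends on these intervals. The endpoints are exploratory, there is no comparator, no test is planned from this model, and the descriptive tables will show the SD at each visit. All of that is correct and limits the weight of the point. The descriptive statistics listed in SAP 4.1 do not include intervals, however, so for these three mean changes the model is the only specified source of confidence intervals.

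**Conclusion.** The point holds as a conditional one. SAP 6.4.2 leaves the within-subject covariance unspecified, and its only written element, taken literally, gives equal variance and equal correlation across visits. Under assumed SDs rising to varying degrees, nominal 95% intervals at Week 12 cover about 86% to 91%, and early intervals cover 97% or more. Under an assumed falling SD the pattern reverses, to about 98% at Week 12 and 90% to 91% at Week 1. With equal SDs coverage is about 94% to 95%. Visit-specific variances give about 95% in every case.

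These figures rest on assumed SDs and correlations, complete data and 50 subjects. The primary endoscopic test, the clinical remission test and every other tested conclusion are unaffected. This is a minor improvement that should be made, because the remedy is standard and protects the intervals whichever way the variance moves.

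**What to change.** In SAP 6.4.2, replace the random subject effect and the maximum likelihood wording with the following: REML; visit as a repeated factor within subject; unstructured covariance; Kenward-Roger degrees of freedom; and no additional random subject effect. State an ordered fallback for non-convergence, for example heterogeneous Toeplitz and then heterogeneous compound symmetry. Both keep a separate variance for each visit.

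The cost is one SAP sentence and a few PROC MIXED options. With five visits an unstructured matrix has 5 × 6/2 = 15 parameters instead of two, and with two visits it has three. The downside is these extra covariance parameters and a possible convergence failure, which the fallback covers. If the variances do prove equal, the interval is only slightly wider: 48.3 against 47.3 under REML in the equal-SD case above.
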